Full Protocol

**Retrospective Analysis of the Use of Biologics for Juvenile Idiopathic
Arthritis Related Uveitis in Abou El Reesh Pediatric Hospital, Cairo
University**

Background and introduction

Juvenile Idiopathic Arthritis (JIA) remains, globally, the most common systemic disorder associated with pediatric uveitis. It accounts for approximately 75% of cases of pediatric anterior uveitis (AU) and affects around 30% of ANA positive JIA patients (regardless their type of arthritis).¹ In a cohort study from the Cairo University Pediatric Hospital, JIA accounted for 39% of all cases of pediatric uveitis (unpublished data).

The uveitis, being asymptomatic, chronic and often severe, leads to complications in a large number of patients. Studies estimate that 28–67% of patients with JIA-associated uveitis develop ocular complications, with 12% developing poor visual outcome. The main causes of poor vision were cataract, band keratopathy and macular edema.²

The only means of improving long term effects of uveitis, is early and aggressive anti-inflammatory treatment.³

The main line of treatment of non-infectious causes of uveitis have been topical and systemic corticosteroids. However, it is well known that their prolonged use often leads to ocular and systemic complications, especially in the pediatric age group.⁴

In 2019, the American College of Rheumatology/Arthritis Foundation recommended that in severe active chronic AU or in the presence of sight-threatening complications, methotrexate (MTX) and a monoclonal antibody TNFi should be administered immediately. This is recommended over MTX as monotherapy. They also recommended that inadequate response to one monoclonal TNFi at standard JIA dose, the dose and or frequency should be increased rather than switching to another monoclonal antibody TNFi.⁵

Immunosuppressive drugs are used as steroid-sparing agents but are not free of complications. They increase the susceptibility of children to infection, may cause organ toxicity, reversible bone marrow suppression and may possibly lead to the development of malignancies.³

Thus, our study aims to analyze the use of biologics in our hospital (Abou el Reesh, Cairo University) for children with JIA in controlling their ocular inflammation, prevention of the development of sight threatening complications and if this outweighs their potential associated side effects.

Patients and methods

Population of study & disease condition

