Retrograde analysis of data of all patients presented to Aboul Reesh uveitis clinic taking biologics from January 2017- January 2020. In our hospital, the rationale for using biologics was a high frequency of sight-threatening, frequent recurrences of uveitis or intolerance to steroids or other immunosuppressive drugs, with severe adverse reactions.

Sample size:

It is expected to review 250 patients files of Aboul Reesh uveitis clinic to find all JIA patients with ocular inflammation treated with biologics.

Inclusion criteria

1. Both genders
2. Age up to 16 years
3. Diagnosed JIA according to rheumatological criteria with ocular affection
 - Any type of arthritis (oligoarticular, polyarticular, systemic onset, ocular JIA)
 - ANA positive or negative
4. Uncontrolled uveitis or frequent relapses

Exclusion criteria:

1. Patients without definitive diagnosis as JIA

2. JIA patients on biologics without ocular affection (for systemic control) or with uveitis controlled without the use of biologics
4. Patients without adequate duration for follow-up (less than 3 months) or lost follow up data
5. Patients without available data prior to the start biologics (to compare control of the uveitis)

Methodology

Data will be obtained from by retrospective analysis of all files of patients with JIA from the Abou El Reesh ophthalmology outpatient clinic.

The patients with ocular inflammation treated by biologics will be further analyzed.

The data analyzed will divided into pre and post biologic treatment:

In both we will document-

-Baseline BCVA (in logMar notation)

- Grading of ocular inflammation

(Anterior chamber and vitreous cells were graded as +0.5, +1, +2, +3 and +4 according to the guidelines of the Standardization of Uveitis Nomenclature Working Group)

- Number of relapses in one year

- Development of sight threatening complication

- Dose and frequency of systemic, regional and topical steroids

- Other interventions required

Treatment parameters to be analyzed include type, duration and dose of biologic agent used, time taken to reach inflammation control, adverse effects, and time taken to develop those adverse effects.

Improvement or worsening of activity of inflammation was assessed according to the Standardization of Uveitis Nomenclature Group's directions (2 step improvement or worsening of cells/flare)

Treatment was determined as efficacious if one of the following was fulfilled:

1. No relapses or decrease in the number of relapses

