2. Decrease in dose of topical or systemic steroids
3. Improvement of BCVA of at least two lines

Statistical analysis plan:

All data will be entered into Excel spreadsheets (Microsoft Corporation, Redmond, WA, USA). All statistical analyses will be performed using IBM SPSS version 22.0 software (IBM Corp., Armonk, NY, USA). Descriptive statistics will be summarized as the mean \pm standard deviation for numerical data, frequencies and percentages for categorical data. The ANOVA -test and Pearson moment correlation will be used to compare the means for the numerical data and to identify correlations between them. Chi-square test will be used to compare categorical data. P-values ≤ 0.05 will be considered statistically significant.

References

- 2) Qian Y, and Nisha R. (2010) Juvenile Idiopathic Arthritis Associated Uveitis. *Curr Opin Ophthalmol.* 21(6): 468–472. doi:10.1097/ICU.0b013e32833eab83

Retrospective Analysis of the Use of Biologics for Juvenile Idiopathic Arthritis Related Uveitis in Abou El Reesh Pediatric Hospital, Cairo University

First version, 1st march 2020

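### Methotrexate and other non-biologic immunosuppressants are not named for extraction and enter no analysis, so the before-and-after result cannot be separated from simultaneous changes in these drugs

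*Combined protocol and SAP*

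**What the plan says.** The Methodology section sets out one list to be filled in for the periods before and after the biologic. It covers visual acuity, inflammation grade, relapses in a year, sight-threatening complications, "Dose and frequency of systemic, regional and topical steroids", and finally "Other interventions required". A separate sentence covers treatment itself: "Treatment parameters to be analyzed include type, duration and dose of biologic agent used", together with time to control and adverse effects. Neither place names a non-biologic immunosuppressant, its dose, or the dates on which it was started, changed or stopped.

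Elsewhere the document shows that these drugs matter. The Background states that "Immunosuppressive drugs are used as steroid-sparing agents" and reports a 2019 guideline under which, for severe or sight-threatening disease, "methotrexate (MTX) and a monoclonal antibody TNFi should be administered immediately". The section on the study population gives the hospital's reasons for using biologics, among them "intolerance to steroids or other immunosuppressive drugs, with severe adverse reactions".

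At the end of the Methodology section, treatment counts as efficacious if any one of three criteria is met. The second is "Decrease in dose of topical or systemic steroids". The statistical analysis plan names descriptive statistics, ANOVA, Pearson correlation and chi-square tests. It has no stratum, covariate or sensitivity analysis for co-medication.

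**The concern.** The study asks what biologics achieve in these children, and its only contrast is each child's record before and after the drug began. Anything else that changed at about the same time is part of that contrast. Non-biologic immunosuppressants are an obvious candidate: the document itself says they reduce the need for steroids, and a steroid reduction alone is enough to classify treatment as efficacious.

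The consequence is one of interpretation. A success rate from this plan describes a treatment regimen whose other components may have been altered in either direction. Nothing in the planned output would tell a reader how many children had such a change, or whether results differ between those who did and those who did not.

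**Working it through.** No arithmetic applies. The documents do not say how many children took an immunosuppressant, or whether it was started, raised, held, reduced or stopped when the biologic began. The check is a comparison of the relevant statements.

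1. **Is the co-drug recorded?** Steroids are specified by dose, frequency and route. The biologic is specified by agent, duration and dose. For immunosuppressants there is only the catch-all at the end of the pre/post list. It applies to both periods and could be read to include them, but it does not ask for drug, dose or dates. Without dates, a change cannot be placed relative to the start of the biologic.

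2. **Is it used?** None of the procedures in the statistical analysis plan refers to it. Even complete recording would leave the planned results unchanged.

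3. **Can it move the endpoint?** Yes, on the document's own account. The Background gives steroid sparing as the purpose of these drugs, and the second efficacy criterion is a steroid decrease. Meeting that criterion is sufficient by itself, and none of the three criteria is conditional on stable co-medication.

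4. **Could it have changed at the same time as the biologic?** The documents support two opposite possibilities. The cited guideline describes methotrexate given with a TNF inhibitor. The local rationale describes children who could not tolerate steroids or immunosuppressants, some of whom may have stopped or reduced the latter as the biologic began.

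5. **What does each pattern do to the comparison?**
   - Started or raised with the biologic: part of any improvement may come from the co-drug, so the comparison favours the biologic. A start shortly before the biologic whose effect appears afterwards acts in the same way.
   - Stopped or reduced: its steroid-sparing effect is lost in the later period, so the comparison works against the biologic.
   - Stable, or never used: little bias from this source.

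6. **Is there another route to separation?** There is no comparator group, so the design supplies none.

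The net effect depends on the mix of these three patterns, which the documents do not give.

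**The case against.** The strongest reply is that the catch-all item already covers these drugs in both periods. That stands in part. A reader might infer that immunosuppressants will go unrecorded, but the documents do not support this: an abstractor could well enter them under that item. What remains is that drug, dose and dates are not required, and that no analysis would use the entries.

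A second reply concerns direction. A reader might infer that the effect of methotrexate will simply be credited to the biologic and the success rate inflated. The documents do not establish that either. Intolerance as a reason for biologics points to children in whom the bias could run the other way. The guideline is weak evidence of local practice: it dates from 2019, while the cohort runs from January 2017 to January 2020, so it cannot show what was done in 2017 and 2018. This reply removes any claim about the sign of the bias. It does not make the effect separable.

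A third reply is that these children had already failed conventional treatment, so a co-drug could add little. Inclusion requires uncontrolled uveitis or frequent relapses, and children controlled without a biologic are excluded. Neither criterion requires prior failure of an immunosuppressant, and neither identifies a child who began both drugs together.

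**Conclusion.** The point holds as a problem of attribution. Non-biologic immunosuppressants are not named for extraction, are at most covered by an undefined item, and are used in no analysis. With no comparator and an efficacy rule that a steroid decrease alone can satisfy, the planned result cannot be separated from simultaneous changes in these drugs.

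Direction and size are both unknown. Any figure for the share of successes due to co-medication would rest wholly on assumed rates of co-starting and of response, for which the documents offer no anchor, so none is given here. If nearly all children were on a stable dose or on none, the bias from this source would be small. The plan as written would not show whether that was so.

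The change is worth making, and it is easiest before files are abstracted, because the plan expects about 250 to be reviewed and a second pass would mean reopening them. It is not a reason to abandon the study.

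**What to change.** - **Extraction.** Add to the pre/post list each non-biologic immunosuppressant, with dose and dates of start, change and stop.
- **Classification.** Group children by co-medication status at the start of the biologic, using a look-back window stated and justified before abstraction: (i) newly started or increased; (ii) stable or none; (iii) stopped or reduced.
- **Reporting.** Give every efficacy outcome overall and for each group, with numbers and confidence intervals. Use group (ii) as a sensitivity analysis for the claim about biologics. It is still an uncontrolled before-and-after comparison.
- **Later changes.** Do not use changes after the biologic began to define the groups. A co-drug added or raised later may reflect inadequate control on the biologic. Moving such children out of group (ii) would leave it enriched for successes. Report a later start or increase separately, as an outcome.
- **Wording.** Describe the overall result as the effect of the biologic with concomitant therapy.

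The cost is a few more extraction columns and one stratified table. No new patients or visits are needed. The groups may be small, with wide intervals, and dates or doses may be missing from some files. The number of children who cannot be classified should be reported.

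### The plan allows time on biologic to be correlated with time to control or to adverse effect, a pairing that can give a positive r with no true link

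*Combined protocol and SAP*

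**What the plan says.** The Methodology section lists the treatment parameters to be analysed, among them "duration and dose of biologic agent used, time taken to reach inflammation control, adverse effects, and time taken to develop those adverse effects". Three of these are times: duration of biologic, time to control and time to adverse effect.

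The Statistical analysis plan gives one sentence on numerical data: "The ANOVA -test and Pearson moment correlation will be used to compare the means for the numerical data and to identify correlations between them". It then sets the threshold: "P-values ≤ 0.05 will be considered statistically significant". It names no pair of variables and rules none out. It has no Kaplan-Meier, Cox or landmark method, and no rule for children who never reach control or never have an adverse effect.

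Length of observation varies between children. The population is patients "taking biologics from January 2017- January 2020", and the only follow-up limit is an exclusion: "Patients without adequate duration for follow-up (less than 3 months) or lost follow up data". Duration is not defined. The plan does not say whether events after stopping the biologic are counted, and the reason for stopping is not on the extraction list.

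**The concern.** An event on treatment can be recorded only if it comes before treatment or observation ends. A child with 6 months on drug can contribute only times below 6 months, while a child with 36 months can contribute times up to 36. Keeping only pairs in which the time is below the duration makes unrelated quantities correlate, even when every date is exact.

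Presence of an adverse effect is tied to duration in two opposing ways. Longer use gives more time for an effect to appear, and an effect that ends treatment shortens use.

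The Background section asks whether the benefit of biologics outweighs their side effects. A finding that longer treatment goes with later control, or with more or fewer adverse effects, could be reported as significant when it comes only from how the times are recorded.

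**Working it through.** The documents give no correlation, event-time distribution or analysed sample size, so there is no planned figure to reproduce. The check is a simulation under stated assumptions.

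**Inputs from the documents**
- Minimum follow-up is 3 months (Exclusion criteria) and the window is 36 months (January 2017 to January 2020). These set the assumed range of durations; an earlier start is not excluded.
- Significance level is 0.05, taken as two-sided because the plan does not say.
- Sample size: "It is expected to review 250 patients files", and in a local cohort "JIA accounted for 39% of all cases of pediatric uveitis". 250 × 0.39 = 97.5, so about 98 JIA files, and those on biologics are fewer. The figures of 30, 40 and 60 children are assumptions below that bound.

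**Assumptions.** Duration D is uniform on 3 to 36 months. Event time T is exponential with mean θ and independent of D, so the true correlation is zero.

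**Mechanism.** Among children with the event, the mean recorded time given duration d is

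E(T | T < d) = θ − d / (exp(d/θ) − 1).

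- θ = 12, d = 6: 12 − 6/0.6487 = 2.8 months.
- θ = 12, d = 36: 12 − 36/19.09 = 10.1 months.
- θ = 2, d = 6: 2 − 6/19.09 = 1.7 months. At d = 36 it is 2.0 months.

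The recorded time climbs with duration when events are slow and hardly moves when they are fast.

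**Correlation of duration with event time.** Only children with T < D enter. Their share is 1 − (θ/33)(exp(−3/θ) − exp(−36/θ)). For θ = 24 this is 1 − 0.727 × (0.882 − 0.223) = 0.52. The sample sizes below are counted before that restriction.

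| Mean event time (months) | Share with event | r | False positives, 30 children | False positives, 60 children |
|---|---|---|---|---|
| 1 | 1.00 | 0.01 | about 5% | about 5% |
| 2 | 0.99 | 0.05–0.06 | 4–5% | about 5% |
| 3 | 0.97 | 0.10 | about 6% | about 9% |
| 6 | 0.89 | 0.22 | 15% | 32–33% |
| 12 | 0.73 | 0.34 | 30–31% | 62–63% |
| 24 | 0.52 | 0.41 | 31–33% | 66–67% |

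Ranges are the spread between simulation runs.

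**Is the cap the cause?** In a separate simulation (Weibull times, shape 1 or 1.5, durations as above):
- With T seen in full, r is 0.00 and rejection is about 5%.
- With events by D only, r is 0.22 to 0.28 at a median of 6 months and about 0.38 at 12 months.
- A Cox score test censored at D (shape 1) rejects in 5.0% to 6.5% of runs.
- Pearson restricted to events in the first 3 months, which every child completes, rejects in 4.9% to 5.5%.
- Entering D as the time for children without the event does not help: r is 0.41 at a median of 12 months.

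**Duration compared by adverse effect, yes or no** (ANOVA, 40 children, no true link):

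| Mean event time (months) | Share of adverse effects that stop the drug | False positives | Difference in duration, with minus without (months) |
|---|---|---|---|
| 24 | none | 67% | +7.1 |
| 24 | a quarter | 21% | +3.7 |
| 24 | half | 4–5% | about +0.4 |
| 24 | all | 65–66% | about −6.4 |
| 120 | none | 20–21% | – |

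At θ = 120 the share with an effect is 1 − 3.636 × (0.975 − 0.741) = 0.15, against 0.52 at θ = 24.

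**The case against.** The plan never says that duration will be set against either event time, or compared between children with and without an adverse effect. Its sentence on numerical data is generic. A reader might infer that every numerical item will be correlated with every other, or that the study will report a spurious link. The text supports neither; these analyses are permitted, not scheduled. This stands and limits the point to what could happen.

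The artefact also depends on speed. If control usually comes within a month or two, inside the 3-month minimum, r is near zero and the error rate is close to nominal. That stands too. It would largely spare time to control. It is less reassuring for adverse effects, which can occur throughout treatment.

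The cap is strict only for events counted on drug or under observation. An adverse effect recorded after stopping escapes it, and the plan is silent on this. Nor do the documents call January 2020 a data cut-off for duration; it dates the patients, and the document is from March 2020.

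Finally, the three efficacy criteria (relapses, steroid dose, BCVA) use neither duration nor the two event times, so the efficacy classification is untouched. These objections narrow the point but do not remove it: the plan invites correlations between numerical items, offers only uncensored methods, and excludes no pair.

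**Conclusion.** The point holds conditionally. If duration is correlated with time to control or time to adverse effect, and events count only on drug or under observation, a positive correlation can arise with no true link. Under the stated assumptions it is negligible at mean event times of 1 to 3 months (false positives about 4% to 9%). From 6 months upward it is material: r = 0.22 to 0.41, with false positives of about 15% to 33% from 30 children and 33% to 67% from 60.

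Comparing duration by presence of an adverse effect is biased in a direction that cannot be known without the reason for stopping. A reader might take a false-positive rate near two thirds as unavoidable. It is not: that rate belongs to the two extremes of stopping at one assumed event rate, and the opposing biases nearly cancel when half of the effects stop the drug.

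All these sizes rest on assumed distributions and sample sizes. They show direction and range and do not forecast this study's results.

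**What to change.** 1. State in the SAP that duration of biologic will not be correlated with, or compared by, time to control, time to adverse effect or presence of an adverse effect. Name the correlations that will be run.
2. Define the start and end of each time, and say whether events after stopping count. Analyse time to control and time to first adverse effect from biologic start by Kaplan-Meier, with Cox regression for any predictor. Censor children without the event at last visit or drug stop, treating stopping as a competing event where it precludes the event of interest.
3. Extract the stop date and, where the file records it, the reason. Report time on drug as drug survival, with stops for failure and for adverse effect shown as competing events by cumulative incidence. Separate Kaplan-Meier curves that simply censor the other reason would overstate each.
4. Otherwise use time on drug only as the exposure denominator.

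The cost is a short SAP revision, two more columns from files already being read, and somewhat more analysis. A few correlations that could not be interpreted are lost. Some reasons for stopping may be missing from retrospective files, and their number should be reported.

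### Time to inflammation control and time to adverse effects are to be summarised by mean ± SD, ANOVA and Pearson, with no handling of children who have had no event by their last visit

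*Combined protocol and SAP*

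**What the plan says.** The Methodology section describes a "retrospective analysis of all files of patients with JIA from the Abou El Reesh ophthalmology outpatient clinic". Among the treatment parameters it lists "type, duration and dose of biologic agent used", followed by "time taken to reach inflammation control, adverse effects, and time taken to develop those adverse effects". Two of these are times to an event.

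The Statistical analysis plan has one rule for each type of variable. The summary is the mean with "standard deviation for numerical data, frequencies and percentages for categorical data". For comparison and association, "The ANOVA -test and Pearson moment correlation will be used to compare the means for the numerical data", while chi-square is used for categorical data. There is no mention of censoring, Kaplan-Meier, log-rank or person-time, and no groups or variable pairs are named for ANOVA or Pearson.

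Follow-up is bounded only from below: exclusion criterion 4 removes children with under 3 months of follow-up or with lost follow-up data. Children followed longer without the event stay in. The population is patients "taking biologics from January 2017- January 2020". The event for time to control is not defined: Methodology defines a "2 step improvement or worsening of cells/flare" but does not say what counts as control.

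**The concern.** A time to event is known only for children who have had the event. With follow-up that starts at 3 months and differs between children, some can be expected to reach last visit uncontrolled, and many without an adverse effect. A rule of mean ± SD then forces an unstated choice.

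- Average only the children with the event (the plain reading). The result says nothing about those never controlled and shifts with length of follow-up.
- Enter the last-visit time for the others. The result blends event times with follow-up length.

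If the choice is left until the data are seen, it can change the reported figure. These two parameters are the plan's only measures of how fast control and harm occur, and the stated aim is to weigh control of inflammation against side effects. An agent that controls every child and one that never controls 30% could show the same mean time to control. Agents with the same effect but different follow-up could show different means.

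**Working it through.** The plan gives no figure to reproduce: the 250 in the Sample size section is a count of files to screen. The check is therefore an illustration.

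**Inputs from the document.** Minimum follow-up 3 months (exclusion criterion 4); calendar window January 2017 to January 2020, which is 36 months; significance at p ≤ 0.05.

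**Assumptions.** Event times T exponential with responder median m = 2, 3, 6 or 12 months. Follow-up C independent of T and uniform on (a, b) = (3, 36), or (3, 18) as a shorter case. The upper limit of 36 is itself an assumption, because the document dates the use of biologics and sets no maximum follow-up. The never-controlled share q is 0 or 30%. Test sizes are 20 per group for ANOVA and 40 for Pearson.

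**Formulas.**
- True responder mean: μ = m / ln 2.
- Share of responders still event-free at last visit: S = μ(e^(−a/μ) − e^(−b/μ)) / (b − a).
- K = μ[(a + μ)e^(−a/μ) − (b + μ)e^(−b/μ)] / (b − a).
- Event-only mean = μ − K / (1 − S). Never-controlled children add nothing to its numerator or denominator, so q drops out, provided non-response is unrelated to length of follow-up.
- Last-visit mean = (1 − q)μ(1 − S) + q(a + b)/2.

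**Worked case, m = 6, follow-up 3-36.** μ = 8.656, S = 0.1814, K = 1.979. Event-only mean = 8.656 − 1.979/0.8186 = 6.24. Last-visit mean with q = 0 is 8.656 × 0.8186 = 7.09; with q = 30% it is 0.7 × 7.09 + 0.3 × 19.5 = 10.81.

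| Responder median (months) | 2 | 3 | 6 | 12 |
|---|---|---|---|---|
| True responder mean | 2.9 | 4.3 | 8.7 | 17.3 |
| Event-only mean, q = 0 or 30% | 2.7 | 3.8 | 6.2 | 8.6 |
| Event-only, monthly visit dating, q = 0 | 3.2 | 4.3 | 6.7 | 9.0 |
| Event-only, three-monthly visit dating, q = 0 | 4.4 | 5.4 | 7.7 | 9.8 |
| Last-visit mean, q = 0 | 2.8 | 4.0 | 7.1 | 10.8 |
| Last-visit mean, q = 30% | 7.8 | 8.7 | 10.8 | 13.4 |
| Truly controlled by 12 months, q = 0 | 98% | 94% | 75% | 50% |
| Truly controlled by 12 months, q = 30% | 69% | 66% | 53% | 35% |

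The event-only mean is about 7/12/28/51% below the true responder mean. Dating control at visits removes or reverses this at medians 2-3 but not at 6-12. No percentage bias is given for the last-visit row with q = 30%, because the mean over all children is then not finite.

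**Adverse effects.** With hazards of 0.05/0.1/0.3/0.6 per year, μ is 240/120/40/20 months. Event-only means are 11.8/11.5/10.4/9.0 months with 3-36 month follow-up and 6.1/6.0/5.7/5.3 with 3-18. A 12-fold range in risk moves the mean by 24% (11.8 to 9.0); the shorter follow-up moves it by 48% at the lowest hazard (11.8 to 6.1) and 41% at the highest (9.0 to 5.3). Crude frequencies reflect risk (8/15/37/58%) but also follow-up (4/8/23/39% with 3-18). Events per unit of patient time are (1 − S) / [μ(1 − S)] = 1/μ, the true rate, in both cases.

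**Tests, if applied to event-only times (simulated).**
- ANOVA, two agents with identical effect, follow-up 3-36 against 3-18 months, medians 3/6/12: false positives about 7/13/16% with q = 0 and 6/9/11% with q = 30%. With equal follow-up and q = 0 they stay near 5%.
- Pearson, time to control against follow-up (unrelated by construction), medians 2/3/6/12: p ≤ 0.05 in about 7/12/33/47% with q = 0 and 5/9/22/31% with q = 30%.
- Log-rank, equal or unequal follow-up and q = 0 or 30%: 4.7-6.1%.
- Kaplan-Meier, n = 40, q = 30%, medians 3/6: average 12-month estimates 0.655/0.525 against true 0.656/0.525.

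**The case against.** The strongest reply is that a mean onset time among affected children is a legitimate conditional description in a retrospective file review. That stands, provided it carries its denominator, which the plan does not require. So a reader who infers that any such mean is invalid, or that time to control will be reported too short, goes further than the document allows. It gives neither typical control times nor a visit interval, so even the direction of the error is not fixed at short medians.

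The tests are hypothetical, because the plan names no groups, no Pearson pair and no analysed sample size. That also stands: the rates above show what would happen if the named tests were applied to these times, and they shrink when some children are never controlled.

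A reader might also infer that the efficacy finding or the whole benefit-harm judgement is compromised. The document does not support this. "Treatment was determined as efficacious if one of the following was fulfilled" introduces a rule based on relapses, steroid dose and visual acuity, and none of its three criteria uses these times. Adverse effects are listed separately from their timing and can be given as frequencies. Nothing says that the benefit-harm judgement rests on the two times.

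None of this supplies a rule for children without the event, and no other part of the document does.

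**Conclusion.** The concern holds for the two time-to-event parameters only. The plan's rule for numerical data does not suit times that are unknown for event-free children. Event-only means cannot show non-response, depend on follow-up, and are unsafe for comparing agents or correlating with duration; last-visit coding moves with both the never-controlled share and follow-up length.

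Size depends on assumptions that the document cannot settle: exponential times, uniform 3-36 month follow-up, and a 0 or 30% never-controlled share. On those, the event-only shortfall runs from about 7% at a 2-month median to about half at 12 months. It is small or uncertain in direction where control is fast, and clear at medians of 6-12 months. For adverse effects, the event-only mean follows length of follow-up more than risk. The change is worth making before extraction; the omission does not undermine the study as a whole.

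**What to change.** For these two parameters only, replace mean ± SD, ANOVA and Pearson with the following, settled before extraction:

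- Kaplan-Meier from start of biologic, censored at last visit, with the control event defined in Standardization of Uveitis Nomenclature terms.
- Numbers with and without the event, the median with 95% CI where reached, and proportions at 3, 6 and 12 months.
- Log-rank for any group comparison.
- Adverse effects per patient and per patient-year.
- A statement that event dates are visit dates, since Kaplan-Meier does not remove that error.
- A denominator beside any mean onset time among affected children.

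Eligibility should stay as it is. The cost is a few sentences in the analysis plan, one event definition, and start, event and last-visit dates for each child. Much of this is already implied by the follow-up criterion and by the listed duration and timing items. The extra analysis is available in standard software. Time-to-control figures may look less favourable, and a median may not be reached if many children are never controlled.
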